## **5 SUBJECT SELECTION AND WITHDRAWAL**

### **5.1 Number of Subjects**

Up to 600 patients will be enrolled to obtain a minimum of two paired data points on 150 subjects.

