#### **7.5 Data Analysis**

This trial will provide baseline data on the performance of SpHb in a population with expected rapid changes in tHb levels. The primary metric to be measured is SpHb's ability to detect critical drops in a trauma population and present the data in a categorical table; statistical significance will be calculated with chi-squared analysis.

The secondary metrics that will be calculated include:

- 1- “Trend capability,” which will be determined by calculating the regression equation and coefficient of determination of a linear mixed effect regression model. The relative differences between data points will be represented graphically with polar plots [Critchley] and 4 quadrant plots.
- 2- Performance of different devices compared to HiCN values (the gold-standard for measuring hemoglobin concentration in blood), including the variability caused by standard of care laboratory devices.
- 3- Absolute accuracy calculation, which will be done by mean test method error with standard deviation, average root mean squared and graphically through Bland-Altman plots [Bland].

Analysis will be performed on the pooled data set as well as separate analyses on all data with high or low signal confidence respectively.

A total of 150 subjects with at least 2 blood samples will be included in the analysis. As a critical drop would require at least two laboratory data points for reference, the study will be powered in order to be 90% confident of achieving that target knowing that 47% of patients recruited in the previous study had at least two paired data points and that it is expected that 20% of patients will be excluded after enrollment (no data points).

An interim analysis will be performed after 50 cases with at least 2 blood samples per case have been completed. This will allow determination of the final sample size in order to obtain an appropriate definition of critical drop detection. The final sample size may be adjusted as a result of this analysis.

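### The only analysis population named in 7.5 requires two blood samples; read literally, it drops single-pair subjects from the accuracy and HiCN comparisons, which need only one pair

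*Combined protocol and SAP*

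**What the plan says.** Section 7.5 (Data Analysis) sets out the primary metric, detection of critical drops, and three secondary metrics: trend capability, performance of the devices against HiCN, and absolute accuracy ("Absolute accuracy calculation, which will be done by mean test method error with standard deviation", root mean square and Bland-Altman plots). It then states: "A total of 150 subjects with at least 2 blood samples will be included in the analysis". The reason follows at once: "As a critical drop would require at least two laboratory data points for reference". No other analysis population is named, and no metric is exempted from this one.

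Three other statements bear on how to read that sentence:

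- Section 7.5 also says: "Analysis will be performed on the pooled data set as well as separate analyses on all data with high or low signal confidence respectively". This sets no minimum number of pairs.
- The planning inputs in 7.5 are that "47% of patients recruited in the previous study had at least two paired data points" and that about 20% of those enrolled will be excluded for having no data points.
- Section 5.1 gives the recruitment aim: "Up to 600 patients will be enrolled to obtain a minimum of two paired data points on 150 subjects".

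Under 7.3 the planned draws are at ED admission and the first morning draw in the ICU, with a third where tests are ordered at ICU admission. Section 7.2 foresees subjects who die during observation, and subjects who never reach the ICU/IMU and have no second sample. For the latter it obtains registry data but does not say whether their one pair is analysed.

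**The concern.** A drop or a trend needs two points in the same patient, so a two-sample rule suits the primary metric and the trend metric. It does not suit the other two. One SpHb reading matched to one reference value is a complete observation for mean error, SD, root mean square and a Bland-Altman plot. One blood sample measured on a hospital analyser and by HiCN is a complete observation for the device comparison.

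If the rule is followed as written, two things are lost. The first is precision, because data already collected go unused. The second is coverage. Given the draw schedule in 7.3, having a second sample depends largely on surviving and remaining on the ICU/IMU pathway. Section 1.1 says that most deaths from early truncal hemorrhage come within 6 to 12 hours of admission, and that the revised sensor was designed for large swings in peripheral perfusion. An accuracy estimate limited to re-sampled patients may leave out some of the patients of most interest.

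**Working it through.** **The plan's own figure.** Section 7.5 asks to be 90% confident of reaching 150 subjects with two pairs, and 5.1 caps enrolment at 600. With a success rate of 0.47 × 0.80 = 0.376, the smallest N with an exact binomial probability of at least 0.90 of reaching 150 is 432. With 0.47 − 0.20 = 0.27 it is 606, and at N = 600 the probability is 0.875. The product reading does not reproduce 600; the subtractive one comes close. Since 600 is stated as an upper limit, neither result shows an error, and nothing below depends on it.

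**Inputs.** From 7.5: 150 subjects, 47% with at least two pairs, 20% with no data. Not in the documents, and therefore assumed: the share with exactly one pair, the number of pairs per included subject, and the within-subject correlation of errors, ρ. The 47% comes from the previous study and the 20% is an expectation for this one, so combining them is itself an assumption.

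**Step 1: single-pair subjects per 150 analysed.** Assume that everyone with data but without two pairs has exactly one.

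- If 47% is of all enrolled: 150 / 0.47 = 319 enrolled; the single-pair share is 1 − 0.47 − 0.20 = 0.33; 319 × 0.33 ≈ 105.
- If 47% is of the 80% with data: 150 / 0.376 = 399 enrolled; the single-pair share is 0.80 × 0.53 = 0.424; 399 × 0.424 ≈ 169.

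These are 105 / 255 = 41% and 169 / 319 = 53% of all subjects with any data.

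**Step 2: precision of the mean error.** Work in units of the variance of one error, with two pairs per included subject. A subject's mean has variance ρ + (1 − ρ)/2, so the information from the 150 is I₀ = 150 / (ρ + (1 − ρ)/2). Each single-pair subject adds 1, so I₁ = I₀ + s. With inverse-variance weighting, the ratio of standard errors (with singles to without) is √(I₀ / I₁).

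| ρ | I₀ | ratio, s = 105 | ratio, s = 169 |
|---|---|---|---|
| 0.3 | 150 / 0.65 = 230.8 | 0.829 | 0.760 |
| 0.5 | 150 / 0.75 = 200.0 | 0.810 | 0.736 |
| 0.7 | 150 / 0.85 = 176.5 | 0.792 | 0.715 |

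The standard error falls by 17.1% to 28.5%.

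**Step 3: how far this depends on the assumptions.**

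- If only half of these subjects have a usable pair, s = 52.5 to 84.5. At ρ = 0.3 and s = 52.5 the ratio is √(230.8 / 283.3) = 0.903. At ρ = 0.7 and s = 84.5 it is √(176.5 / 261.0) = 0.822. The cut is about 10% to 18%.
- If each included subject gives three pairs (7.3 allows a third sample for some), then at ρ = 0.3 I₀ = 150 / (0.3 + 0.7/3) = 281.3. With s = 105 the ratio is 0.853, so the smallest full-share gain drops from 17% to about 15%.

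**The case against.** The strongest reply is that the sentence is a sizing statement and not an inclusion rule. It opens the sample-size paragraph, and the next sentence treats 150 as a target to be reached ("the study will be powered in order to be 90% confident of achieving that target") and links two samples to critical drops alone. Elsewhere 7.5 speaks of a pooled data set, and the only exclusion after enrolment that it describes is for subjects with no data points; a single-pair subject has one. This stands as a fair alternative reading. A reader might infer that the plan expressly discards single-pair subjects from every metric. The documents do not say so. But on the sizing reading, accuracy and HiCN have no stated population at all, and an analyst could choose one after seeing the data. Either reading calls for the same edit.

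A reader might also infer that the analysis is capped at 150 and that evaluable subjects beyond that number are lost. The documents do not support this: 5.1 and 7.5 treat 150 as something to obtain, 7.5 allows the final size to change after the interim analysis, and 600 is only an upper limit on enrolment.

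Three further objections stand in part.

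- The 105 to 169 range is not a figure of the plan. It rests on the assumption stated in Step 1.
- A single ED sample does not guarantee an SpHb pair. Section 7.1 places the sensor only after the patient's position is stabilised and the secondary survey is done, while 7.3 times the first draw at ED admission, so some first samples may have no matching reading. That is why the half-share case is shown. It does not affect hospital-analyser-versus-HiCN comparisons, which need no SpHb value.
- The two metrics are secondary and descriptive. No acceptance limit or test is set for them, so better precision changes no planned decision. This limits the weight of the point. It does not answer the selection issue.

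**Conclusion.** The point holds as a mismatch between the one population named in 7.5 and two of the metrics listed above it. Followed literally, the two-sample rule excludes subjects who can contribute to absolute accuracy and device-versus-HiCN performance, and favours those who survived and stayed to be sampled again. Neither the direction nor the size of any resulting bias can be worked out from the documents, and a pair may be missing for reasons unrelated to outcome, such as no valid SpHb reading.

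The precision at stake is a reduction of about 17% to 28.5% in the standard error of the mean error if all subjects with data but without two pairs have one usable pair, and about 10% to 18% if half do. Both ranges assume two pairs per included subject and ρ between 0.3 and 0.7. The primary metric is unaffected. The change should be made, because it corrects a stated rule at almost no cost, but it is not critical to the study's main conclusion.

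**What to change.** In 7.5, replace the single population sentence with one population per metric, for example:

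*Critical-drop and trend analyses include every subject with at least two paired data points. Absolute-accuracy and device-versus-HiCN analyses include every enrolled subject with at least one usable pair, and allow for repeated and unequal numbers of pairs per subject. For SpHb, a usable pair is a reference sample with a matching valid SpHb reading.*

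Use the term paired data point throughout, since 7.5 moves between blood samples and paired data points, and a sample without a valid SpHb reading is not an SpHb pair. Report accuracy and HiCN results in the two-or-more-pair subset as a sensitivity analysis, so that readers can see whether re-sampled patients differ.

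The cost is one short text edit and one extra table, with no new patients, draws or visits.

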## **2 STUDY HYPOTHESIS**

SpHb can be used to identify bleeding patients sooner than standard of care by identifying critical drops between laboratory samples.

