#### **7.3 Sample Collection**

Blood samples will be collected at time of ED admission and first a.m. lab draw in ICU. The blood samples will be based on clinical need and sent to at least two reference devices: the standard of care reference device for patient, hospital laboratory devices located at MHH, and a cyanomethemoglobin (HiCN) analyzer and a hematology analyzer located at a Masimo facility. For those subjects who have laboratory tests ordered at time of ICU admission, a third sample will be collected and sent to the CeTIR research lab for preparation for the cyanomethemoglobin analyzer at a Masimo facility. The collection of the HiCN and hematology analyzer samples must follow standard laboratory practices for handling of blood products as detailed in the manual of operations with at least 1 mL of blood being collected in an EDTA tube. Each sample will have a unique identifier with the identification key revealed by the site only after the sample has been processed by the Masimo analyzer. The exact time of sampling will be documented for retrospective analysis along with type (venous or arterial) and site of blood sampling, location of patient, time since presentation, and specific hospital laboratory analyzer used.

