#### **7.4 Data Collection**

While the patient is in the Emergency Room, data will be collected and stored on a Radical-7. In the operating room and intensive care unit, data collection will be done using a Radical 7 connected to a laptop computer which will store live data [REDACTED]. All data will be properly labeled and downloaded to a server as soon as it is available for retrospective analysis.

Information to be collected will come from the trauma registry and medical records and will include subject demographics (gender, age, race/ethnicity), injury details (type of injury, severity, location on body), pre-hospital EMS care, initial ED care (blood products, life- saving interventions, vital signs), surgical and interventional radiology procedures, major complications (i.e. ARDS, sepsis, MOF), discharge location, number of hospital, ventilator and ICU days, and quantity and timing of blood product administration, anesthetics, changes in oxygenation, blood pressure cuff location, notes about any movements during surgery.

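### Section 7.5 judges critical drops from laboratory values that may be many hours apart and ignores red cells given in between, so its table cannot by itself support the hypothesis about bleeding patients

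*Combined protocol and SAP*

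**What the plan says.** Section 2 sets the target: "SpHb can be used to identify bleeding patients sooner than standard of care by identifying critical drops between laboratory samples". Section 7.5 turns this into a hemoglobin endpoint: "The primary metric to be measured is SpHb's ability to detect critical drops in a trauma population". The results go into a categorical table, and "statistical significance will be calculated with chi-squared analysis".

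The only reference named for a critical drop is the laboratory: "As a critical drop would require at least two laboratory data points for reference". Section 7.3 gives the timing: "Blood samples will be collected at time of ED admission and first a.m. lab draw in ICU". A third sample is added for subjects who have tests ordered on reaching the ICU. The exact time of each sample is recorded. Under Section 7.2 the device stays on for up to 24 hours.

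Section 7.4 records "quantity and timing of blood product administration", as well as surgical and interventional radiology (IR) procedures. Section 7.5 uses none of these items. Apart from the pooled data set, its only split is "separate analyses on all data with high or low signal confidence respectively".

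The size of a critical drop is not given. It is deferred to the interim look after 50 cases: "This will allow determination of the final sample size in order to obtain an appropriate definition of critical drop detection". No sentence says whether SpHb is scored continuously between draws or only at the draw times.

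**The concern.** The population is highest-level trauma activations expected to need ICU or intermediate care (Section 5.2). Section 1.1 puts most deaths from early truncal hemorrhage within 6–12 hours of admission. The gap between arrival and the first morning draw can cover the period in which bleeding happens and is treated.

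The claimed advantage of SpHb is that it sees drops the laboratory has not yet seen. Those are the events that transfusion can remove from a laboratory reference before the next draw. A patient who bled, showed a fall on SpHb, received red cells and had a restored second value enters the table as having had no drop. Conversely, a patient diluted by fluids without bleeding can enter as having dropped.

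At stake is whether the primary table, however favourable or unfavourable, can be read as evidence about bleeding patients.

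**Working it through.** **The plan's own figures.** Section 7.5 states no sensitivity, specificity, drop prevalence or transfusion rate, so there is no performance figure to reproduce. Its numbers (150 subjects, 47%, 20%, 90%) concern recruitment. Only N = 150 is used below.

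**Assumed inputs.** One interval per subject; true critical drop from bleeding in a share p = 10%, 20% or 30%; SpHb sensitivity 0.80 and specificity 0.90 against the true event; a share m = 10%, 25% or 50% of true drops reversed by transfusion before the second draw, independently of whether SpHb detected them. Let D = 150p.

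**Case A: SpHb scored continuously between draws.**
- Correct detections counted as false positives: 0.80 × D × m
- All false positives: 0.10 × (150 − D) + 0.80 × D × m
- Reference-negatives: (150 − D) + D × m
- Apparent specificity: 1 − false positives / reference-negatives
- Apparent positive predictive value (PPV): 0.80 × D × (1 − m) / [0.80 × D + 0.10 × (150 − D)]

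Example with p = 20% and m = 25%: D = 30. Miscounted detections are 0.80 × 30 × 0.25 = 6.0. False positives are 12.0 + 6.0 = 18.0. Reference-negatives are 120 + 7.5 = 127.5. Specificity is 1 − 18.0/127.5 = 85.9%. PPV is 18/36 = 50.0%, against 24/36 = 66.7% without masking.

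| p | m | Miscounted detections | False positives / reference-negatives | Apparent specificity | Apparent PPV |
|---|---|---|---|---|---|
| 10% | 0 | 0 | 13.5 / 135 | 90.0% | 47.1% |
| 10% | 10% | 1.2 | 14.7 / 136.5 | 89.2% | 42.4% |
| 10% | 50% | 6.0 | 19.5 / 142.5 | 86.3% | 23.5% |
| 20% | 0 | 0 | 12.0 / 120 | 90.0% | 66.7% |
| 20% | 10% | 2.4 | 14.4 / 123 | 88.3% | 60.0% |
| 20% | 25% | 6.0 | 18.0 / 127.5 | 85.9% | 50.0% |
| 20% | 50% | 12.0 | 24.0 / 135 | 82.2% | 33.3% |
| 30% | 0 | 0 | 10.5 / 105 | 90.0% | 77.4% |
| 30% | 10% | 3.6 | 14.1 / 109.5 | 87.1% | 69.7% |
| 30% | 50% | 18.0 | 28.5 / 127.5 | 77.6% | 38.7% |

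**Case B: SpHb read only at the draw times.** A drop reversed by the second draw is absent from both methods. It adds no false positive and leaves specificity unchanged. The D × m treated bleeders (7.5 of 30 at p = 20%, m = 25%) simply sit among the subjects without a drop, and the table carries no information about them.

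**Dilution.** Suppose 10% of non-bleeders show a dilutional reference drop, with no masking. At p = 20% this is 0.10 × 120 = 12 subjects, and 12/(30 + 12) = 29% of reference-positives are not bleeding. At p = 10% and 30% the share is 13.5/28.5 = 47% and 10.5/55.5 = 19%. These count correctly as hemoglobin drops (Section 7.5) but wrongly if read as bleeding (Section 2).

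**The case against.** The strongest reply is that Section 7.5 contains no scoring rule to criticise. The drop is undefined and the SpHb window is unstated, so the undefined endpoint is the deeper gap. That is fair, but defining a threshold would not cure this problem: any threshold applied to a value taken after transfusion can still miss the bleed.

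A reader might infer four stronger things that the documents do not support.

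- That correct detections will count as false positives. This follows only under continuous scoring. Section 2 points that way, but the paired-data wording in Sections 5.1 and 7.5 equally allows draw-time scoring.
- That the primary result is biased under either rule. Under draw-time scoring, SpHb change and laboratory change cover the same interval. The stated metric is not biased; the table only says less about bleeding.
- That dilution corrupts the primary metric. A dilutional fall is a real drop that SpHb should detect.
- That treatment between draws is ignored altogether. It is ignored in the analysis, but blood product timing and procedures are collected. Sampling is also not fixed at two draws: the text says at least two, and a third draw can shorten the interval and reduce masking.

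Restricting the primary table to intervals without transfusion is also tempting. It would discard the treated bleeders the study is about, and would select on treatment given after enrolment in a study that Section 3 describes as non-blinded.

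What remains is the mismatch between the hypothesis and the reference, and the absence of any rule for transfused intervals.

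**Conclusion.** The point stands as a gap between the bleeding hypothesis and the table meant to test it. Section 7.5 pools intervals with and without red cells between draws and leaves unused the data that would separate them.

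Under continuous scoring, and on the assumed inputs, 1.2 to 18 correct detections among 150 subjects are miscounted, and apparent specificity falls from 90% to between 89% and 78%. At the light end the effect is negligible. Under draw-time scoring there are no added false positives, and the loss is silence about the treated bleeders. Prevalence, masking, sensitivity and specificity are all assumptions, because the documents give none of them. The direction under continuous scoring is firm; the size is not.

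This is an inexpensive improvement worth making before analysis. It does not show that the study's hemoglobin comparison is invalid.

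**What to change.** In Section 7.5:

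1. State the SpHb scoring window: continuous between draws, or at the draw times only.
2. Keep every interval in the primary table, and also report that table split by whether red cells were given between the two draws. The draw times in Section 7.3 and the product timing in Section 7.4 are enough to do this.
3. In transfused intervals, do not use the post-transfusion value to call an SpHb reading taken before the transfusion either a false positive or a true negative. Show these readings as a separate category, so that the rule neither flatters nor penalises the device.
4. Add a secondary table of SpHb drop against bleeding status, defined from data already collected: red cells given, or hemorrhage-control surgery or IR, within the monitoring window. State that in a non-blinded study this reference may be influenced by the displayed SpHb.

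Write these rules before the interim look that is to settle the drop definition. The cost is wording, two extra tables and smaller numbers per stratum. No new data are needed. Section 7.4 names no intravenous fluid volume, so dilutional drops will stay unlabelled, and the report should say so.

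### Section 7.5 ties the undefined critical-drop endpoint to a 50-case interim without limiting that look to laboratory values or setting those cases aside, so the primary table could be optimistic

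*Combined protocol and SAP*

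**What the plan says.** Section 7.5 names SpHb detection of critical drops as the primary metric, to be shown in a categorical table and tested by chi-squared. On the reference side it says only "As a critical drop would require at least two laboratory data points for reference". No laboratory threshold, SpHb threshold, time window or alpha appears in the supplied text.

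The interim is described in three consecutive sentences of Section 7.5: "An interim analysis will be performed after 50 cases with at least 2 blood samples per case have been completed"; then "This will allow determination of the final sample size in order to obtain an appropriate definition of critical drop detection"; then "The final sample size may be adjusted as a result of this analysis". The final analysis set is given as "A total of 150 subjects with at least 2 blood samples will be included in the analysis", a description that the interim cases also meet.

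Section 2 gives the hypothesis: "SpHb can be used to identify bleeding patients sooner than standard of care by identifying critical drops between laboratory samples". Section 3 calls the study non-blinded. The one masking step found is in Section 7.3, which has "the identification key revealed by the site only after the sample has been processed by the Masimo analyzer". Section 7.5 also describes the study's purpose: "This trial will provide baseline data on the performance of SpHb in a population with expected rapid changes in tHb levels".

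**The concern.** Every cell of the primary table depends on what counts as a drop and what counts as SpHb detecting it. The only sentence about defining this attaches it to a look at study data. Section 2 has SpHb finding drops between laboratory samples, so a full definition needs an SpHb rule as well as a laboratory one.

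If those rules are picked because SpHb performs well in the first 50 cases, and the same 50 are then counted in the result, part of the apparent performance is selection. Sensitivity, specificity and the chi-squared result would look better than they should, even for a device that works. Separately, if SpHb results steer the final sample size, the chi-squared test no longer holds its nominal level.

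**Working it through.** **Readings of the interim sentence.**
- (a) Only the sample size is reset. The following sentence, which names sample size as the thing that may change, supports this.
- (b) Cut-offs are chosen at the interim. The words about a definition of detection leave this open.
- (c) The sample size is set so that a definition can be drawn from the whole sample.

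The supplied text does not choose between them. The sample key in Section 7.3 does not settle it, because it is released once each sample has been processed.

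**Inputs.** From the plan: interim at 50, analysis of 150, cap of 600, and rates of 47% and 20% (Sections 5.1 and 7.5). The plan states no figure for this bias, so there is none to reproduce. All else is assumed: laboratory and SpHb changes bivariate normal with mean -1 and SD 1.5 g/dL, correlation 0.4 to 0.8, alpha 0.05, 20,000 simulated trials per scenario. The candidate cut-offs are illustrations, not proposals.

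**Measure.** Youden's J = sensitivity + specificity - 1. Excess = J observed in all 150 for the chosen definition, minus the population J of that same definition. The choice is made in the first 50 by largest chi-squared in the positive direction.

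| Choice made in the first 50 | Excess in J, all 150 | 95% CI wholly above truth |
|---|---|---|
| None (fixed 2 g/dL for both) | about 0 | about 3-4% |
| SpHb cut-off only, laboratory fixed at 2 g/dL | 0.028-0.035 | 6.2-7.8% |
| 3 shared cut-offs | about 0.04 | 5.0-8.6% |
| 5 shared cut-offs | about 0.05 | 6.5-10.5% |
| 5 laboratory x 5 SpHb cut-offs | 0.055-0.070 | 11.5-14.0% |

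The standard error of J is 0.07 to 0.10. Over four assumed distributions and three selection rules, the excess is 0.25 to 0.82 standard errors. It is about zero in the later 100 subjects. With a laboratory-only choice it is within 0.004 of zero, all 150 kept.

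**Cross-check with a different model** (laboratory change plus independent SpHb error; best J chosen in the first 50). Only the first 50 carry the selection, so the excess in 150 should be near 50/150 of theirs:
- SpHb cut-off only: 0.101 x 50/150 = 0.034, simulated 0.033.
- Both cut-offs: 0.204 x 50/150 = 0.068, simulated 0.067.

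**Reading (c).** If the definition is chosen on all 150, selection touches every subject. The excess is then 0.065-0.067 (3 shared cut-offs), 0.083-0.084 (5) or 0.091-0.116 (5x5).

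**Chi-squared when SpHb is unrelated to the laboratory.** Choosing cut-offs in the first 50 and testing all 150 rejects in about 6 to 8% of trials with 3 or 5 shared cut-offs and 10 to 11% with 5x5, against about 5% in the later 100.

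**Resizing on SpHb results, definition fixed.** Write Z(N) = sqrt(50/N) Z(50) + sqrt(1 - 50/N) Z', with Z' an independent standard normal. For each Z(50), take the N in the allowed range that maximises the chance that |Z(N)| > 1.96, and average over Z(50). One upper limit is the expected evaluable number at the cap: 600 x 0.47 x 0.80 = 225.6, so 226. The limit of 300 is assumed.

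| Allowed final N | Worst-case rejection, no association |
|---|---|
| 150-226 | 5.5% |
| 150-300 | 5.8% |
| 100-226 | 6.3% |
| 50-150 | 9.4% |
| 50-226 | 10.0% |
| 50-300 | 10.3% |

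Section 7.5 gives no floor and no direction for the adjustment, so the lower rows cannot be excluded.

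**The case against.** The strongest reply is that the sentence literally speaks of determining the sample size, and the next sentence repeats that. No sentence says that cut-offs are chosen at the interim, still less on SpHb performance. This stands: a reader might infer that the plan sets out to tune its endpoint, and the documents do not support that. What survives is that the text does not exclude it.

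A reader might also infer that the study's accuracy results are inflated. They are not. Section 7.5 uses the word accuracy for the mean-error, root-mean-square and Bland-Altman metrics, which use no cut-off.

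The purpose is modest: a non-interventional study producing baseline data, with no stated success criterion. That makes Type I error secondary, but baseline detection rates are estimates, and optimism in them still matters. The plan also names only a categorical table and chi-squared; Youden's index is used here to summarise that table.

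Every magnitude rests on assumed distributions and cut-offs, and the largest figures for the interim choice need a search over the laboratory definition too. That is fair; the simpler search, over the SpHb cut-off alone, gives about 0.03.

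Finally, absence cannot be proved. The text between Sections 3 and 5 was not available, the revision history is redacted, and the manual of operations was not supplied. A definition may exist there.

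**Conclusion.** The concern holds in a conditional form. In the supplied text the primary endpoint has no definition, the definition is linked to an interim on study data, and no rule says which data that look may use, how the sample size may change, or whether the 50 cases count in the final table.

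If cut-offs are chosen at the interim on SpHb performance and those cases are kept, the detection table is biased upward by an average of about 0.03 to 0.07 in Youden's index. That is under one standard error, but enough to raise the share of intervals lying wholly above the truth from 3-4% to about 5-14%. A laboratory-only choice, or reporting on later subjects, removes the bias.

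Resizing alone should not be called harmless. Its worst case is about 5.5-5.8% only if the final number cannot fall below 150, and about 9-10% if it may fall to 50, provided that SpHb results drive the change.

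This should be fixed. Confidence is medium, because the intended reading cannot be established from the documents.

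**What to change.** **Preferred.** In Section 7.5, state the laboratory threshold, the SpHb threshold and the time window, or cite them if they exist elsewhere. They should be fixed and dated before SpHb is compared with laboratory values. Replace the interim text with wording such as: At 50 evaluable cases only the frequency of laboratory hemoglobin drops is examined; no comparison of SpHb with laboratory values is made or reported before then; any change in the final sample size follows a stated rule on that frequency alone, within the cap of 600. The sponsor must supply that rule.

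Word this as a restriction on the analysis, not as masking. Under Section 9.3 device data and case report forms go to the sponsor after each study visit, so a claim that SpHb is masked would not match the data flow.

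**Alternative, if SpHb data must inform the definition.** Call the first 50 a development set and report the primary table on later subjects only. With 150 evaluable in total, 100 remain. The CI is sqrt(150/100) = 1.22 times as wide, about 22% wider. For a fixed 2 g/dL definition, simulated power falls from about 81% to 65% at an assumed correlation of 0.4, and from 99% to 96% at 0.6.

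**Cost.** Either option needs an amendment signed by the principal investigator and the sponsor and approved by the IRB (Section 11.2). The preferred option loses no subjects and no precision.
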